7.3 AE Severity Grading Scale

The severity of AEs is evaluated using the 5-level criteria of NCI CTCAE v4.03.

For adverse event terms not included in NCI CTCAE version 4.03, graded according to the following CTCAE classification principles:

- Grade 1 Mild; asymptomatic or mild signs; clinical or diagnostic observations only; medical intervention not indicated.

- Grade 2 Moderate; minimal, local or non-invasive intervention required; limiting age-appropriate instrumental activities of daily living (e.g., cooking, shopping, using the telephone and managing money, etc.).
- Grade 3 Severe or medically significant but not immediately life-threatening; hospitalization or prolonged hospitalization indicated; disabling; limiting self-care activities of daily life (e.g. bathing, dressing and undressing, feeding self, using the toilet, and taking medications), but not bedridden.
- Grade 4 Life-threatening consequences; urgent intervention indicated.
- Grade 5 Death related to AE.

7.4 Correlation Between AEs and Investigational Drug

The relationship between the investigational drug and AEs can be determined using the followings:

Table 5. Correlation determination between AEs and investigational drug

Correlation	Criteria
Definitely Related	
 ● The AE occurrence has a reasonable time relationship with administration time; ● The investigational drug can more reasonably explain the AE than the other causes (such as concurrent disease, environment, toxicity, or other treatment received); ● The AE resolves or is alleviated after treatment interruption or dose reduction; ● The event meets the recognized pharmacological AE type; ● The AE does not occur after re-administration.
Probably Related	
 ● The AE occurrence has a reasonable time relationship with administration time; ● The investigational drug provide more reasonable explanations on the AE than the other causes (such as concurrent disease, environment, toxicity, or other treatment received); ● The AE resolves or is alleviated after treatment interruption or dose reduction (if applicable);
Probably Unrelated	
 ● Other causes provide more reasonable explanations on the AE than the investigational drug (such as concurrent disease, environment, toxicity, or other treatment received); ● The AE does not resolve or be alleviated after treatment interruption or dose reduction (if applicable), or the situation is unclear; ● The AE does not occur after re-administration or the situation is unclear.
Definitely Unrelated	
 ● The AE occurrence has no reasonable time relationship with administration time, or ● Other causes provide evident explanations (such as concurrent disease, environmental, toxicity, or other treatment received by the subject).

Correlation	Criteria
Unable to Determine	
 ● The above information is unclear and the AE cannot be determined based on the available information. Further follow-up information is not accessible to the investigator.

7.5 Recording of AEs

The investigator shall document AEs and SAEs using medical terms and concepts. Avoid colloquialisms/abbreviations. All the AEs (including SAEs) shall be documented on the AE forms in the eCRFs.

7.5.1 Collection and time of AEs

The investigator shall use non-leading questions when asking the subjects about AEs.

All the AEs, including SAE, that occur after the signing of the ICF within 90 days since the last dose shall be collected, regardless of whether it is observed by the investigator or self-reported by the subject.

Within 90 days since the last dose, if the subjects receive other anti-tumor therapy, any AEs related to the study drugs shall be collected, and be followed-up until the adverse reactions return to grade 0-1 or baseline.

After 90 days since the last dose, the investigator should report any SAEs that are considered related to the study drugs.

7.5.2 AE Follow-Up

The AE shall be followed until the events return to the baseline values or grade 0–1, or until the investigator believes that no further follow-up is required for reasonable reasons (if the event cannot be resolved or has already been improved). If the event cannot be resolved, a reasonable explanation shall be documented in the eCRF. The outcome of an AE/SAE and date shall be documented in the eCRF and medical record, regardless of whether the event is related to the study drugs.

7.5.3 Contents of AE documentation

The investigator must document all the AEs, including the diagnosis (document signs and symptoms including the laboratory abnormalities if there is no diagnosis), time and date of occurrence (if applicable), CTCAE grade of severity and changes in severity (events \geq grade 3), whether it is an SAE, whether it is an AE of special interest (AESI), measures taken for the study

drugs, treatment for the AE and outcome of the event, and relationship between the event and study drugs.

For an SAE, the investigator shall also provide the date when the AE meets the criteria for an SAE, the date when the investigator is informed of the SAE, the reason of being an SAE, date of hospitalization, date of hospital discharge, possible cause of death, date of death, whether an autopsy has been performed, causality assessment of the study procedures, causality assessment of other drugs, and other possible causes of the SAE. The investigator shall provide the rationales of the causality and a description of the SAE. In the SAE description, the followings shall also be included: the subject number, age, gender, height, and weight; indication for receiving the investigational drug, cancer staging, and overall condition; SAE occurrence, development, outcome, and result; laboratory results related to the SAE (the time of the examination, units, and normal ranges must be provided); medical history, onset and duration of concurrent diseases related to the SAE; medication history and initiation, duration, and dosage of concomitant medications related to the SAE; initiation, duration, and dosage of the investigational drug.

Descriptions of the AE are as follows:

Diagnosis, signs, and symptoms

Document the definite diagnosis, if there is one, rather than just listing the independent signs and symptoms (e.g. hepatic failure rather than jaundice, elevated transaminase, and asterixis). Signs and symptoms shall be reported as separate AEs/SAEs if cannot be attributed to the diagnosis. If it is determined that the signs and symptoms are caused by the diagnosis, then only the diagnosis shall be reported, included the signs and symptoms. The record of signs and symptoms shall then be deleted. A follow-up SAE report shall be submitted.

AEs secondary to other events

Generally, AEs secondary to other events (such as result of another event or clinical sequelae) shall be documented as the primary event, unless the event is severe or an SAE. However, clinically significant secondary events shall be recorded as independent adverse events in the eCRFs if they occur at different time than the primary event. If the relationship between events is unclear, document them as separate events in the eCRFs.

Ongoing or recurrent AEs

An ongoing AE refers to an event that does not resolve and is ongoing between two assessment time points. These AEs shall only be documented once in the eCRFs. The initial severity shall be documented, and the information shall be updated if the event exacerbates.

Recurring AEs refer to AEs that have resolved between the two time points of assessment but subsequently occur again. These events shall be independently documented in the eCRFs.

Laboratory abnormalities

Any clinically significant laboratory abnormalities shall be reported as AEs. The investigator is responsible for reviewing all the laboratory abnormalities, and determine whether the findings shall be reported as AEs.

Death

During the entire course of the study, all the deaths that occur within 90 days after the last dose shall be documented in the eCRFs and Mortality Report Form and reported to the sponsor timely, regardless of the causality with the study drugs.

If the cause of death is known, record the cause of death as an AE and the outcome of the event as a death and submit an SAE report; if the cause of death is unclear, the AE shall be recorded as Death of Unknown Cause in the AE form, and submit the SAE report as Death of Unknown Cause. The exact cause of the death shall be further investigated.

If the cause of death is confirmed to be PD, then the event shall not be documented and reported as an AE/SAE. However, the event shall be documented in the Mortality Report Form of the eCRF and reported to the sponsor timely.

Pre-existing medical conditions

Symptoms/signs present during the screening period will be recorded and reported as AEs only if their severity, frequency, or property becomes aggravated (except for worsening of the studied disease). The relative changes shall be documented, such as increased frequency of headaches.

Hospitalization and prolonged hospitalization, or surgery

Any AEs leading to hospitalization or prolonged hospitalization shall be recorded and reported as SAEs, with the following exceptions:

- Hospitalization or prolonged hospitalization as required by study protocol (such as for dose administration or efficacy evaluation).
- Hospitalization due to a pre-existing medical condition that remains stable, e.g. elective

surgery/therapy scheduled prior to the study.

However, elective surgery/therapy required because of the exacerbated condition during the study (e.g. surgery/therapy required earlier than scheduled) shall be considered as an AE.

PD

PD is defined as the worsening of subject condition caused by the primary tumor that the study drug is targeting, the appearance of new lesions, or the progression of the primary lesion. PD will not be reported as an AE. Any deaths, life-threatening events, hospitalization or prolonged hospitalization, permanent or significant disability/incapacity, congenital anomaly/birth defects, or other important medical events caused by PD will not be reported as an SAE.

Overdose

An overdose is the administration of a drug at more than the dose specified in the study protocol. All the occurrences of overdose must be documented in the eCRF.

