7.1 Definition of AEs

An AE is defined as any adverse medical event that occurs after the signing of the informed consent form within 90 days since the last dose of the study treatment, regardless of whether or not considered as related to the study drugs. AEs include but are not limited to the followings:

- Worsening of pre-existing (prior to enrollment) medical conditions/diseases (including symptoms, signs, and laboratory abnormalities);
- Any new adverse medical conditions (including symptoms, signs, and newly diagnosed diseases);
- Clinically significant laboratory abnormalities.

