### **5.6.1 Adverse Events**

All adverse events will be coded using MedDRA dictionary for lower level term (LLT), preferred term (PT), high level term (HLT), high level group term (HLGT) and system organ class (SOC). AE

reporting period will be further defined based on onset date/becoming serious/becoming more severe as:

- Pre-treatment AE: AE occurs/becomes serious/becomes more severe before first dose of treatment and after inform consent.
- Treatment-emergent AE: AE occurs/becomes serious/becomes more severe on or after date of first dose of treatment up to last dose of study treatment+90 days
- Post treatment AE: AE occurs/becomes serious/becomes more severe on or after date of last dose of study treatment+91 days

If onset date of AE is missing or partial missing, determination of AE reporting period will be based on rules in Section 4.3.

- **Overview of adverse event**

Listing will be provided for pre-treatment and post-treatment AE.

Number and percentage of subjects who experience AE and event frequency will be summarized for:

- Treatment emergent period
  - TEAE
  - Treatment related AE (TRAE)
  - Serious AE (TESAE)
  - AE leading to death
  - TRSAE
  - TRAE leading to death
  - TEAE leading to treatment discontinuation
  - TRAE leading to treatment discontinuation
  - Important AE (Chinese regulator specific requirement only)
  - Immune-related AE (irAE)

Unless otherwise stated, SOC/PT summary will be sorted according to descending order of frequency.

- **TEAE analysis**

Number and percentage of subjects with AE will be summarized by:

- SOC and PT and by highest CTCAE grade for TEAE

- SOC and PT and by highest CTCAE grade for TRAE
- SOC and PT and by highest CTCAE grade for TEAE leading to treatment discontinuation
- SOC and PT and by highest CTCAE grade for TRAE leading to treatment discontinuation
- SOC and PT and by highest CTCAE grade for important AE (Chinese regulator specific requirement only)
- PT for TESAE
- PT for infusion-related reactions(IRR)
- **Immune-related treatment emergent AE and AE of special interest**

Immune-related treatment emergent AE:

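### SAP 5.6.1 classifies AEs by when they worsened, but Protocol 7.5.3 does not require that date, so AEs that start in screening and worsen on IBI308 can be classed as pre-treatment

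*Protocol*

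**What the plan says.** **SAP 5.6.1** assigns each AE to a pre-treatment, treatment-emergent or post-treatment period by when it began, became serious or became more severe. The treatment-emergent rule reads "AE occurs/becomes serious/becomes more severe on or after date of first dose of treatment up to last dose of study treatment+90 days" and has no grade floor. Pre-treatment AEs are listed; the incidence tables cover the treatment-emergent period. If the onset date is missing or partial, 5.6.1 refers to SAP 4.3. It gives no rule for a missing date of worsening.

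**Protocol 7.5.1**: "All the AEs, including SAE, that occur after the signing of the ICF within 90 days since the last dose shall be collected". AEs that start in screening are therefore in scope, and Table 1 schedules AE evaluation at screening.

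**Protocol 7.5.3** contains three relevant rules:
- The required content of an AE record includes the date of occurrence and "CTCAE grade of severity and changes in severity". A parenthesis directly after these words refers to events of grade 3 or higher. No date is requested for a change in severity.
- For an ongoing AE: "These AEs shall only be documented once in the eCRFs". The next sentence is "The initial severity shall be documented, and the information shall be updated if the event exacerbates".
- For pre-existing conditions: "Symptoms/signs present during the screening period will be recorded and reported as AEs only if their severity, frequency, or property becomes aggravated", and then "The relative changes shall be documented, such as increased frequency of headaches".

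**Protocol 7.1** counts as an AE "Worsening of pre-existing (prior to enrollment) medical conditions/diseases (including symptoms, signs, and laboratory abnormalities".

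**The concern.** The analysis rule depends on a date that the data-collection rules do not ask for. An AE that began after consent but before the first dose, and then worsened on treatment, is treatment-emergent by the SAP's definition. If the only required date on its single record is a screening onset, the analysis has no specified way to recognise this.

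Treatment-emergent, treatment-related, immune-related and special-interest event rates are the core of the safety report in a single-arm trial with no comparator. Low grades matter here: under Protocol 7.8.2, grade 2 is enough for diarrhea/colitis, uveitis and interstitial pneumonia to be AESIs. A step from grade 1 to grade 2 can decide whether an event is in the AESI table.

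**Working it through.** The documents state no figure to reproduce. The check follows one event through the two recording routes that the protocol allows.

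**Test case.** Grade 1 diarrhea starts after consent and before the first dose, does not resolve, and becomes grade 2 after the first dose.

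**Route A: 7.5.1 with the ongoing-AE rule of 7.5.3**
1. The event falls in the collection window, so it is entered as an AE with a screening onset.
2. It is unresolved, so it stays one record.
3. When it worsens, that record is updated. The rise to grade 2 is captured, but no sentence requires its date.
4. In the SAP, the onset is before the first dose. Whether the worsening came on or after the first dose decides the class, and that date need not exist.
5. The referral to SAP 4.3 covers onset dates only. Section 4.3 in any case leaves a wholly missing date unimputed.
6. Classified on the only required date, the event is pre-treatment and is listed.

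**Route B: the pre-existing-conditions paragraph of 7.5.3, supported by 7.1**
1. The symptom is present in screening, so it is not recorded as an AE at that point.
2. When it is aggravated, it is recorded and reported as an AE and the change is documented.
3. The natural onset date is the date of aggravation, which is after the first dose.
4. In the SAP it is treatment-emergent, and at grade 2 it also counts as an AESI.

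The same clinical course gives two classifications. Section 7.1 does not settle which route applies: an event arising between consent and enrollment is an AE in its own right, because it follows consent, and is also a condition that pre-dates enrollment.

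**Comparison with other missing data.** SAP 4.3 counts missing causality as related and missing grade as grade 3 or higher. An undated worsening has no equivalent conservative rule.

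**Scale.** The amendment summary gives 28 enrolled subjects. Assuming all 28 were dosed and so form the safety set, k misclassified subjects change a given preferred-term or AESI row by k/28:

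| k | k/28 |
|---|---|
| 1 | 3.6 points |
| 2 | 7.1 points |
| 3 | 10.7 points |

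These values of k are illustrative. The documents give no count of screening-onset AEs that worsened. The any-TEAE row does not move for a subject who has another TEAE.

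**The case against.** The strongest reply is that the protocol captures more than this suggests. The ongoing-AE rule requires an update on any exacerbation, with no grade limit, so the higher grade is recorded. Section 7.1 and the pre-existing-conditions paragraph allow an aggravation to be an AE in its own right with an on-treatment onset. AEs are reviewed before Cycle 1 and at each visit, Protocol 9.2 asks for prompt data entry with an audit trail, and all AEs are listed with a treatment-emergent flag. The eCRF and its completion guide are not among the documents and may hold a date for each grade change.

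Much of this stands, and it rules out several stronger readings that a reader might infer:
- *That 7.5.3 dates severity changes at grade 3 and above but not below.* It names no date of change at any grade. The parenthesis is also ambiguous, since it may cover events that reach grade 3.
- *That these events necessarily drop out of the tables and that harm is understated.* This depends on the eCRF design and on the route each site followed. It is a risk, not a demonstrated result.
- *That the date of becoming serious is also missing.* Section 7.5.3 already requires the date on which an AE met the SAE criteria.
- *That worsening after day 90 creates a mirror-image error.* After day 90, 7.5.1 asks only for drug-related SAEs, and under 7.5.2 a grade 1 event already meets the follow-up endpoint. The documents give this little support.

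The AESI effect is also narrow. Grade 2 is enough for only three groups of terms, and known interstitial lung disease, inflammatory bowel disease and most active autoimmune disease are excluded at entry.

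The reply does not close the gap. An audit trail dates the data entry, not the clinical worsening. Visit records allow a query but do not replace a rule. A treatment-emergent flag is only as good as the date behind it. Route B is one permitted reading, and 7.5.1 with the ongoing-AE rule still leads to the other. The exclusions do not prevent ordinary grade 1 diarrhea in screening.

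**Conclusion.** The protocol and SAP do not fit together on this point. The SAP classifies by date of worsening at any grade; the protocol does not require that date, and the SAP has no fallback when it is absent. Separately, 7.5.1 and the pre-existing-conditions paragraph of 7.5.3 conflict for symptoms that arise in screening. An AE that starts at low grade in screening and worsens on IBI308 can therefore be listed as pre-treatment when it should be tabulated as a TEAE, or as an AESI for grade 2 diarrhea/colitis, uveitis or interstitial pneumonia.

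The size is unknown. Each affected subject moves a given row by 3.6 points if the safety set is 28, and the any-TEAE row may not change. The conclusion assumes that the eCRF follows the protocol text and has no separate date for grade changes; if it has one, the dating gap narrows to a documentation point and the conflict between the two rules remains. The primary ORR analysis is unaffected.

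**What to change.** **Protocol 7.5.3**
- Remove the grade 3 limit on severity changes, and record the grade and date of every severity increase.
- State that an AE present before the first dose that worsens on or after it gets a new record, with the date of worsening as onset, as an exception to the one-record rule.
- Limit the pre-existing-conditions paragraph to conditions present before consent was signed, so that it no longer conflicts with 7.5.1.

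**SAP 5.6.1**
- Class an undated worsening of a screening-onset AE as treatment-emergent, in line with the conservative handling of missing causality and grade in SAP 4.3.

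**Subjects already enrolled**
- Query the date of worsening for every screening-onset AE whose grade rose.

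**Cost.** One eCRF field or line, a short text change in each document, and a small query round given 28 subjects. TEAE and AESI rates may come out slightly higher.

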7.6 Expedited Reporting of SAEs and Pregnancy

SAE reporting:

SAEs should be reported from the signing of informed consent to 90 days (inclusive) after the last dose of investigational drug administration. The investigator must fill out the "CFDA SAE Report Form", regardless of whether it is the initial report or a follow-up report, and sign and date the form. The investigator must report the SAE to the sponsor, CFDA, and ethics committee within 24 hours of noticing the event. Refer to the table below for contact details.

For SAEs occurring outside of the above-mentioned period, those considered related to the investigational drug shall also be reported to the sponsor.

The investigator must submit the completed SAE report form to the sponsor within 24 hours of noticing the event. The investigator shall urgently perform visit on missing information and provide a complete SAE report for events that result in death or are life-threatening.

The investigator shall also report the event to the CFDA, health administration departments, and EC in accordance with the regulations.

Table 6. SAE report contacts

Organization	Contact Person	Fax/Telephone/Address
Hospital Name	EC	Hospital Fax/Telephone

Innovent Biologics (Suzhou) Co., Ltd.	Clinical Study Department PV	[contact] Email: [contact]
Office of Drug Research and Supervision, Department of Drug and Cosmetics Registration, China Food and Drug Administration		Address: [name] Postal Code: 100053 [contact] [contact]
Medical Administrative Department, Health Administration		Address: [name] [contact] [contact]
Province, Autonomous Region, Municipality Food and Drug Administration	Based on the requirements of the Food and Drug Administration Department of each province, autonomous region or municipality	

Pregnancy

The risk of embryotoxicity exists for the similar kind of drugs. All the subjects with childbearing potential must take effective contraceptive measures.

During the study, if a female subject becomes pregnant, she must be withdrawal from the study. The investigator must report to the sponsor within 24 hours of noticing the event and submit the Innovent Clinical Study Pregnancy Report/Follow-Up Form.

During the study, if a female partner of a male subject exposed to the study drugs becomes pregnant, the subject will continue in the study. The investigator must report to the sponsor within 24 hours of noticing the event and submit the Innovent Clinical Study Pregnancy Report/Follow-Up Form.

The investigator must continuously monitor and follow-up the outcome of the pregnancy until 8 weeks after the subject gives birth. The outcome shall be reported to the sponsor.

If the outcome of the pregnancy is stillbirth, spontaneous abortion, fetal malformation (any congenital anomaly/birth defects), or medical abortion, it shall be considered a SAE and the event requires to be reported in accordance with SAE procedures and time limits.

If the subject also experiences a SAE during the pregnancy, the CFDA SAE Report Form shall also be filled out and reported according to SAE's procedures.

